8.6. Concomitant Medications

Simple analgesia (Ibuprofen, Aspirin, Paracetamol, co-codamol) are permitted and will be recorded via the database at screening (Visit 1) and throughout the trial. Use of prescribed opiates for a non TMD event should be reported in the database and a risk assessment considered if the participants are receiving Treatment As Usual, to determine if there are any risks associated with contraindicated medications. All repeat medications will also be recorded in the clinical notes and database.

8.7. Assessment of Compliance

Participants' compliance on the TAU (oral medication) arm will be assessed by the trial team at each research assessment through verbal enquiry as part of the e-CRF: used medication (y/n and why not if no); used as per dosing regimen (y/n and why not and at what regimen if no). Following prescription of trial medication, the participant will be contacted via an ePRO form or telephone to check they have commenced taking the medication and the date it started.

As the oral IMPs represent no higher risk than the standard of care participants will return their unused oral trial medication to their local pharmacy for disposal unless they are discussing with their GP continuation of the medication. At visit 5 (week 36) participants will be asked if they used all the trial medication and at what dosing regimen and why they took this/these decision(s).

Injectable IMP packaging will not be returned to the pharmacy, but unused injectable IMP will be returned, if appropriate, or disposed of locally in line with local Trust procedures. Clinicians will document the administration of the injection in the participant's clinical record.

Compliance in the TAU arm of the trial is potentially difficult to assess, as participants may take varying amounts of medication to treat their condition. Despite this variation they may still be considered compliant for trial purposes as the variation may be the best method, they have identified to relieve symptom burden whilst managing any adverse effect profile. To provide an objective decision on compliance for the trial for participants in the TAU arm, an assessment of compliance will be made following the completion of the week 36 visit for each participant. The IMP data collected across the 36 weeks will be looked at independently by three clinicians, each with a special interest in the field of facial pain, who will each record their assessment on whether each participant in the TAU arm has been compliant with their prescribed treatment based on their CPI data and responses to the e-CRF data points on use of medication. Each clinician will independently report their findings, and if there are any inconsistencies between the findings for individual participants, the clinicians will discuss these and come to a consensus. Participants who are not considered to have been compliant with their treatment will be identified to the statistics team for analysis purposes.

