3.3.1. Primary Endpoint/Outcome

The trial's two co-primary outcomes for effectiveness are:

- Characteristic pain intensity (CPI) assessed by a composite average, worst and current numerical rating scale of pain (0-100 scale (Von Korff et al., 1992)) at 36 weeks of treatment examining last 12 weeks' pain intensity.
- Disorder-specific related quality of life (the Oral Health Impact Profile for TMDs [OHIP-TMD (Yule et al., 2015)]) at 36 weeks of treatment examining the last 4 weeks' quality of life.

The trial's primary economic outcome is:

- incremental cost per quality-adjusted life year gained of the most effective treatment compared to other treatments at 36 weeks calculated using data from the Health Utilisation Questionnaire (HUQ) (administered baseline, 12, & 36 weeks), the time and travel questionnaire (T&TQ administered at census date of 24 weeks), the EQ-5D-5L (administered at baseline, 12, 24 & 36 weeks), and routine sources and study specific estimates for unit costs (Jones and Burns, 2021).

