The co-primary outcomes of disorder specific quality of life measured by OHIP-TMD, and pain intensity measured by CPI at 36wks will each be compared between treatment groups using separate linear mixed effects regression models with nested random effects for site and participant and fixed effects for treatment, timepoint, treatment by timepoint interaction, baseline score and the stratification factor of psychosocial status. These models will each include the outcome data at all timepoints which will help account for missing data (under a missing at random assumption). These models will each be used to calculate mean differences at 36 weeks (BTX - TAU and Lidocaine injections - TAU) and associated two-sided 95% confidence intervals (CIs) for each coprimary outcome to test the superiority of BTX and Lidocaine injections compared to TAU. Superiority will be concluded if the upper limit of the two-sided 95% CIs are both less than 0. To conclude that BTX or Lidocaine are effective, statistically significant differences in both co-primary outcomes compared to TAU will be needed. This analysis will be conducted in the ITT population.

These models will also each be used to estimate the mean differences (BTX - TAU and Lidocaine injections - TAU) and associated two-sided 95% CIs for the secondary outcomes of disorder specific quality of life measured by OHIP-TMD, and pain intensity measured by CPI at 12 and 24 weeks.

²The hypothetical strategy targets the treatment effect in the hypothetical setting where the intercurrent event would not occur.

A secondary analysis will additionally adjust the estimates for OHIP-TMD by including fixed effects for the baseline covariates of GCPS and duration of pain that are known to be strongly related to outcome. This will also be done for CPI. However, as CPI is a component of the GCPS, baseline GCPS will not be included. We will consider alternative strategies to deal with the intercurrent events of treatment discontinuation and alternative treatments in the SAP.

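### TAU compliance is decided after week 36 partly from CPI, a co-primary outcome, so any supplementary comparison using that flag would condition on outcome in one arm

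*Protocol*

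**What the plan says.** Section 8.7 explains that TAU compliance is hard to assess because intake may legitimately vary, and sets up a three-clinician panel with this aim: "To provide an objective decision on compliance for the trial for participants in the TAU arm". On timing, "an assessment of compliance will be made following the completion of the week 36 visit for each participant". Each clinician records "whether each participant in the TAU arm has been compliant with their prescribed treatment based on their CPI data"; in full, the stated basis is "based on their CPI data and responses to the e-CRF data points on use of medication". The clinicians report independently and resolve differences by consensus. On use, "Participants who are not considered to have been compliant with their treatment will be identified to the statistics team for analysis purposes".

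For the injection arms the same section describes no panel, only that "Clinicians will document the administration of the injection in the participant's clinical record".

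Section 3.3.1 lists as one of the two co-primary outcomes "Characteristic pain intensity (CPI) assessed by a composite average, worst and current numerical rating scale of pain", assessed at 36 weeks. Nothing in 8.7 restricts the panel to earlier CPI values.

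Sections 10.2.1 and 10.2.2 place the co-primary and secondary analyses in the ITT population under a treatment policy strategy. Section 10.1 defines only ITT and safety populations. Section 10.2.1 adds: "We will consider alternative strategies to deal with the intercurrent events of treatment discontinuation and alternative treatments in the SAP".

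**The concern.** A compliance label should describe exposure. Here the raters see the pain scores, including the week 36 score being analysed, before deciding who complied. Two TAU participants with identical intake could receive different labels because one has more pain. Section 8.7 calls the decision objective, but an input that is itself the outcome works against that.

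The label exists in one arm only. Excluding, censoring or conditioning on it would remove TAU participants partly according to their CPI while leaving the injection arms whole, and the comparison would no longer be protected by randomisation. Because the protocol itself fixes the data source, the timing and the arm, a SAP that adopted the flag would inherit the problem.

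Descriptive use is affected differently. Section 3.2(c) sets an objective on responder rates and adherence over time in all interventions. If the flag supplied TAU adherence, some participants would be misclassified, and adherence and CPI response would share an input. The protocol does not say the flag will be used this way.

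**Working it through.** **The plan's own figures.** Inputs from section 10.3: OHIP-TMD SD 20.7, difference 6.0, 90% power, two-sided 5%, baseline correlation 0.6, attrition 27%; CPI SD 20, minimally important clinical difference 10.

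- n per arm = 2 × (1.960 + 1.282)² × 20.7² / 6² = 250.1, rounded up to 251.
- 251 × (1 − 0.6²) = 160.6, so 161.
- 161 / (1 − 0.27) = 220.5, so 221; 3 × 221 = 663.
- CPI with 161 per arm: SE = 20 × √(2/161) = 2.23; 10/2.23 − 1.96 = 2.53; power 99.4%.

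The plan's 663 and its CPI power above 99% both reproduce. The point does not depend on them; they supply the scale.

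**Size of the bias if flagged TAU participants are excluded.** Assumptions that are not in the documents:

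- a share q of TAU is flagged;
- the panel's latent judgement correlates w with week 36 CPI;
- compliance is otherwise unrelated to outcome;
- the CPI baseline correlation is 0.6 (the protocol gives 0.6 only for OHIP-TMD);
- there is no true treatment difference.

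Without baseline adjustment the TAU mean shifts by SD × w × φ(z₁₋q)/(1 − q):

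- q = 20%, w = 0.3: 20 × 0.3 × 0.280/0.80 = 2.10 points.
- q = 20%, w = 0.5: 20 × 0.5 × 0.280/0.80 = 3.50 points.
- q = 30%, w = 0.5: 20 × 0.5 × 0.348/0.70 = 4.97 points.

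Baseline adjustment removes roughly a fraction 0.6² of this: 2.10 × 0.64 = 1.34, 3.50 × 0.64 = 2.24, 4.97 × 0.64 = 3.18. A baseline-adjusted simulation (161 per arm before exclusion, 4,000 trials per setting, a single week 36 analysis in place of the planned mixed model) gave:

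| Flagged | Correlation w | Bias in CPI difference (injection − TAU) | Two-sided rejection rate, CPI alone |
|---|---|---|---|
| 20% | 0 | 0.1 | 4.9% |
| 20% | 0.3 | 1.3 | 12.0% |
| 20% | 0.5 | 2.3 | 23.3% |
| 30% | 0.5 | 3.3 | 39.0% |

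Across q = 10–40% and w = 0.2–0.7 the bias ran from 0.5 to 6.0 points. With w = 0 it was about zero and the rejection rate 4.8–5.0% throughout.

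**Direction.** The table assumes that high pain is read as non-compliance, which works against the injections. If low pain after stopping medication is read as non-compliance, the sign reverses: −1.45 points at 20%/0.3 and −3.2 at 30%/0.5.

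**Carry-over to OHIP-TMD.** With an assumed CPI–OHIP correlation of 0.5 and no baseline adjustment, the bias was 1.8 points at 20%/0.5 and 2.6 at 30%/0.5, against a minimally important clinical difference of 6.

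**The case against.** The strongest reply is that nothing in the protocol uses the flag. Both co-primary outcomes and all secondary outcomes are analysed by ITT under treatment policy, and there is no per-protocol population. A reader might infer that the trial's main conclusion is at risk; the documents do not support that.

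A reader might also take the sentence in 10.2.1 on alternative strategies as a commitment to use the panel's decision. It concerns treatment discontinuation and alternative treatments, which section 7.6 records separately. Use of the flag there is possible but not stated.

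It is tempting to say that the rule flatters TAU. Section 8.7 says only that varied intake may still count as compliant because it may be how a participant manages symptoms and adverse effects. It does not say that high pain leads to a non-compliant label, and the sign depends on the raters.

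It is also tempting to call the damage permanent. It is not: medication use, regimen followed, reasons and start date are collected (8.7), and dosages and tapering are documented in the eCRF (8.4), so an exposure-only flag can be rebuilt.

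Finally, CPI is one of two inputs, and injections are given and recorded at scheduled visits, so the absence of a panel for those arms is not itself a fault.

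All of this stands and narrows the point. What it leaves untouched is that the protocol names the outcome as an input to the label and sends the label for analysis.

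**Conclusion.** The point holds in a limited form. Section 8.7 builds a co-primary outcome into a TAU-only compliance label. The ITT co-primary and secondary results are unaffected. Any supplementary treatment comparison that excludes, censors or conditions on the label would be biased if the raters give CPI any weight; a descriptive adherence summary would suffer misclassification instead.

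The illustrative bias of about 1.3 to 3.3 CPI points is 13% to 33% of the 10-point minimally important clinical difference. It rests on assumed flag rates, correlations and CPI baseline correlation, and on a simplified model. The unadjusted shifts for the same settings, 2.1 and 5.0 points, overstate what a baseline-adjusted analysis would show by more than half. Direction cannot be determined from the documents. The rejection rates concern CPI alone, not the plan's rule requiring both co-primary outcomes.

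**What to change.** In section 8.7, strike CPI data from the stated basis of the panel's decision. Give the three clinicians a listing of exposure data only: drug, dose, dates, whether medication was used, whether it was used as per the regimen, and reasons. Withhold CPI, OHIP-TMD and all other outcomes.

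Re-adjudicate on the same basis any participant already assessed, ideally with raters who have not seen the CPI data. For any analysis based on compliance, define injection-arm compliance from recorded administration, as the number of the three scheduled cycles received.

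The cost is one amended sentence, a restricted listing and possibly some repeat adjudication. No new data are needed and the sample size of 663 does not change. The raters lose some clinical context. Adjudication follows each participant's own week 36 visit, so an early change leaves fewer decisions to repeat.

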9. PHARMACOVIGILANCE

9.1. Definitions

Term	Definition				
Adverse Event (AE)	Any untoward medical occurrence in a participant to whom a medicinal product has been administered, including occurrences which are not necessarily caused by or related to that product.				
Adverse Reaction (AR)	An untoward or unintended response in a participant to an investigational medicinal product which is related to any dose administered to that participant.				
	The phrase "response to an investigational medicinal product" means that a causal relationship between a trial medication and an AE is at least a reasonable possibility i.e. the relationship cannot be ruled out.				
	All cases judged by either the reporting medically qualified professional or the Sponsor as having a reasonable suspected causal relationship to the trial medication qualify as adverse reactions				
Reference Safety Information (RSI)	The RSI is a list of medical terms detailing the ARs that are expected for an IMP and must be referred to when assessing a SAR for expectedness.				
Serious Adverse Event (SAE)	 A serious adverse event is any untoward medical occurrence that: Results in death Is life-threatening* Requires inpatient hospitalisation or prolongation of existing hospitalisation. Results in persistent or significant disability/incapacity Consists of a congenital anomaly or birth defect Other important medical events that jeopardise the participant or require intervention to prevent one of the above consequences. * - life-threatening refers to an event in which the participant was at immediate risk of death at the time of the event; it does not refer to an event which hypothetically might have caused death if it were more severe. 				
Serious Adverse Reaction (SAR)	An adverse event that is both serious and, in the opinion of the reporting Investigator, believed with reasonable probability to be due to one of the trial treatments, based upon the information provided.				
Suspected Unexpected Serious Adverse Reaction (SUSAR)	A serious adverse reaction, the nature and severity of which is not consistent with the approved Reference Safety Information.				

9.1.1. Assessment of severity of AEs

The PI, or delegated clinician, should make an assessment of severity for each AE according to the following criteria:

Grade 1: Minor adverse event, not requiring medical intervention. May be asymptomatic and is likely to be a clinical or diagnostic observation only; or may be a symptomatic but minor, or transient event, with no necessity for medical intervention. This might include asymptomatic laboratory or radiographic findings. A minor adverse event is likely to have only marginal clinical relevance.

Grade 2: An adverse event which may require some medical intervention (local/non-invasive) and which is symptomatic to patient. May affect activities of daily living.

Grade 3: Significant symptoms reported, requiring medical intervention, and possibly requiring hospitalisation. Medically significant and likely to be significantly affecting activities of daily living.

Grade 4: An adverse event that requires urgent intervention or may have life-threatening consequences.

Grade 5: Death related to the adverse event.

9.1.2. Assessment of seriousness of AEs

The PI, or delegated clinician, should make an assessment of seriousness against the standard definition in the Safety Reporting Definitions section 9.1

9.1.3. Assessment of causality of AEs

The relationship between the use of IMP and the occurrence of each AE must be assessed and categorised by the PI or delegated clinician using clinical judgement to determine the causal relationship. Other factors such as medical history of underlying diseases, concomitant therapy and any other relevant risk factors should be considered. The PI should also consult the current version of the Reference Safety Information as per section 8.1 and make a determination according to the definitions below:

Yes (related)	Event considered related to IMP
Probable	It is probable the event is related to IMP
Possible	It is possible the event is related to IMP
Unlikely	It is unlikely the event is related to IMP
No (unrelated)	Event considered unrelated to IMP
Unable to	After review of information available the PI/delegated clinician is unable to
determine	determine if event is related to IMP or not

9.2. Recording and Reporting AEs and SAEs

All AEs occurring from point of consent to end of trial participation must be recorded in the AE eCRF page as well as the participant's clinical notes.

For all AEs the following will be recorded: severity, seriousness, causality, and any concomitant medication used.

All SAEs occurring from point of consent to end of trial participation must be reported to NCTU on an SAE form and also recorded in the AE eCRF page and recorded as serious.

All SARs occurring from the 1st dose of IMP to the time periods specified in table 2 must be reported to NCTU on an SAE form and also recorded in the AE eCRF page.

Table 2 - Half-lives of IMPs and time period from last dose to end of SAR monitoring

Medication	Half life /hrs	Cleared (5 half lives) /hrs	Source	Time period from last trial dose (including any tapering dose) for end of SAR monitoring/days*
Oral amitriptyline	25	155	https://www.medicines.org.uk/emc/product/14334/smpc	7
Oral gabapentin	7	35	https://www.medicines.org.uk/emc/ product/158/smpc	7
IM Lidocaine 2%	1.68	8.4	https://pubmed.ncbi.nlm.nih.gov/74 39378/	7
IM Botox	10	50	https://www.ema.europa.eu/en/doc uments/referral/botox-article-29- referral-annex-i-ii-iii_en.pdf	7

^{*}Rounded up to nearest week. If pregnancy falls outside of this time period, it would not need to be reported for the trial or monitored for adverse effects

Following this defined active monitoring period for SARs, investigators are still required to report any SARs or SUSARs they become aware of.

All SAEs/SARs must be reported to NCTU on an SAE Form via secure email to [contact] as soon as possible and within 24 hours of research staff becoming aware of the event.

Preliminary reporting to NCTU via email or telephone is acceptable in order to meet the 24-hour reporting timeline, where circumstances do not allow for immediate completion of the SAE form. However, the SAE form should be completed and submitted as soon as possible after the initial notification in order to comply with reporting timelines.

For each SAE the following information will be collected:

- Full details in medical terms and case description
- Event duration (start and end dates, if applicable)
- Action taken

- Outcome
- Seriousness criteria
- Causality in the opinion of the investigator

In addition, for each SAR an assessment of whether the event is considered expected or unexpected in the opinion of the chief investigator (or delegate if unavailable), in accordance with the approved reference safety information (section 8.1), is required.

Any change of condition or other follow-up information should be submitted to NCTU at [contact] as soon as it is available or at least within 24 hours of the information becoming available via the SAE Follow-up form. Events will be followed up until the event has resolved or a final outcome has been reached.

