	To compare the proportion of participants achieving more than 30% and more than 50% reductions in pain intensity, as well as 30% and 50% improvements in quality of life, across treatment groups at 36 weeks	Disorder-specific quality of life measured by Oral Health Impact Profile-TMDs (OHIP-TMD) and Characteristic Pain Intensity (CPI) at baseline and 36 weeks.
	To examine responder rates and adherence over time in all interventions	Routinely collected descriptive data. Longitudinal sequential qualitative data collection from purposive subsample of participants.
	To evaluate whether any of the interventions affect jaw function	Jaw function limitation questionnaire short-form administered at screening, 12, 24 and 36 weeks.
	To evaluate whether any of the interventions affect psychosocial distress, sleep quality, or analgesia use	PHQ-4, psychosocial distress administered at screening, 12, 24 and 36 weeks. Brief Pittsburgh Sleep Quality Index administered at screening, 12, 24 and
		36 weeks. Over-the-counter (OTC) analgesia use. Data collected from patient at screening, 12, 24 and 36 weeks
	To compare the adverse effect profiles of the interventions including changes in the	Structural TMJ changes on MRI and apparent diffusion coefficient as a marker of bone density. Serum

IRAS ID: 1008152

	1	T	
	temporomandibular joint (TMJ) using MRI and biomarkers.	biomarkers of bone turnover (CTX and P1NP). Measured from screening visit (visit 1) up to 36 weeks.	
	To explore treatment experiences and acceptability of interventions	Longitudinal sequential qualitative data collection from participants	
		Global impression of change at 36 weeks.	
		Liverpool adverse effects profile. AE or SAE reporting from informed consent up to 36 weeks.	
Exploratory	Explore participants' reporting	Pain tolerance and threshold to a	
	accuracy of pain intensity in response to a controlled pressure	pressure stimulus and participant's reported pain intensity.	
	stimulus.	R ² values derived from regression of	
	Explore the influence of pain reporting accuracy on outcome in	applied stimulus and reported pain intensity.	
	the trial.		
Investigational Medicinal Product(s)	Oral gabapentin		
	Oral amitriptyline		
	As this is a pragmatic trial any brand of the oral medication can be used		
	Injectable therapy to bilateral masset	er and temporalis muscles:	
	- Intra-muscular lidocaine 2%,	2mls with or without preservative	

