7.4.4. Further visits (3, 4, and 5)

All participants will have completed the research assessments ahead of the follow-up visit as described in 7.4.6 and if not, further copies will be issued for completion prior to commencing the follow-up visit. Consent will be reconfirmed at each follow-up visit. Follow up and or further treatment will occur at visits 3 (week 12 + - 7 days), 4 (week 24 + - 7 days) and 5 (week 36 + - 7 days).

Follow up visit 3 at week 12 (+/- 7 days), visit 4 at week 24 (+/- 7 days) and follow up visit 5 at week 36 (+/- 7 days), will be conducted in person for all treatment arms. A clinical assessment will take place here, as well as a vital signs assessment. Participants allocated to Botox or Lidocaine will also receive their next cycle of injections at visits 3 and 4. Participants allocated to TAU will have their medication reviewed by the trial investigator and changes made, if required, at visits 3 and 4. Their GP will be written to, if necessary, to ask them to alter their prescription, based on the decision of the trial investigator. Treatment may also be provided by the site pharmacy, depending on local processes.

At the 36 weeks, patients will be returned to the care of their GP as per usual standard of care practice. The GP will discuss and agree with the patient how their care will be conducted after the trial. The research team will contact the patient by telephone 7 days after the 36 week visit to identify any adverse events in that time period. Two attempts will be made to contact the participant.

Case report forms will be completed as required at each trial visit to capture any changes in the medical history, migraine history (if relevant), and if receiving injectable therapy examination status of any facial nerve weakness using the House-Brackmann regional and global scores (Reitzen et al., 2009).

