^b All research assessments will be collected up to 7 days ahead of any IMP administration at these visits and prior to administration of any further IMP. New local prescriptions will be issued by the GP following instruction from the site teams at weeks 12 and week 24, or by sites for their pharmacy at 12 weeks and at 24 weeks for the patient to collect in the TAU arm.

^c All research assessments will be collected up to 7 days ahead of any IMP administration at these visits and the CRF updated at the visit.

^d Confirmed in writing in the clinical notes at each study visit.

^e Pregnancy test required at 36 weeks for all participants of childbearing potential or 7 days after this point if participants are still on TAU week 36^e

fMigraine history and MIDAS only repeated if positive at any of the previous visits. If reporting a new headache then ID-Migraine, migraine history and MIDAS are completed at that visit and the migraine history and MIDAS are repeated at subsequent visits.

§ Phone call to collect AE data in 7 days since week 36 visit. Only required if participant still receiving TAU IMP at week 36 or stopped IMP after week 35.

^h Qualitative interview will ideally take place during screening but may be up to 4 weeks after consent to the interview. This may be after the start of the IMP in some cases.

TAU prescription may be issued at any point during screening or at Day 0 as appropriate. Day 0 is the first dose of IMP.

Review of medication only at week 36

IMPORTANT: If participants who discontinue trial treatment plan to begin a new therapy for TMD (NHS or private) within the remainder of the trial monitoring period, they should be asked if they will complete the next set of research assessments prior to beginning a new treatment in routine clinical care and then go back on schedule to the next scheduled set of research assessments following this.

Key
AE & SAE - Adverse Event & Serious Adverse Event
BPSQI - Brief Pittsburgh Sleep Quality Index
CN V & VII - 5th Cranial Nerve and 7th Cranial Nerve
CPI (within GCPS) - Characteristic Pain Intensity (Graded Chronic
Pain Scale)
EQ-5D-5L - See section 7.4.6.4
FaCE - Facial Clinimetric Evaluation
GIC - Global impression of change

HUQ – Health Utilisation Questionnaire
MIDAS – Migraine Disability Assessment Test
LAEP - Liverpool adverse events profile
OHIP-TMDs - Oral Health Impact profile for TMD
PHQ-4 - Patient Health Questionnaire-4
PMH – Past Medical History

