- Issues of tolerability will be discussed with the patient and recorded in the CRF with a possible step back to the previous dose to see if a longer duration at this dose is either more effective or allows upward titration due to accommodation of any adverse effects.
- Discontinuation: unless an emergency the *quickest* allowed discontinuation would be spread over 4 weeks or slower for amitriptyline and gabapentin in similar increments or smaller than upwards titration dose steps. Much slower tapering off over a number of months of either drug is permissible and often required/desirable.

The same standardised sites and doses for the injectable IMPs will be used for both injectable IMPs and all patients. These are based on data suggesting they are the sites with the widest safety margins for adverse effects from the injectable IMPs (Hu et al., 2010; Lee et al., 2017; Peng and Peng, 2018). Bilateral masseter and temporalis will be injected for all patients.

The sites for injection are detailed in figures 1 and 2. All injections should be provided bilaterally using a 27-30 gauge 12.7-13mm detachable needle with a graduated 1.0ml syringe following skin cleaning in accordance with local aseptic non touch technique policy. The needle ideally can be replaced after one side has been injected. Figure 3 demonstrates the injection sites without penetration of skin in a volunteer.

Figure 1 Masseter – a) Anatomical structures; b) Positioning of injection sites with anatomy; c) Positioning of injection sites without anatomy

[figure not shown]

a) Safest zones in masseter are estimated using four anatomical lines – superior line, ear lobe to commissure; inferior line, mandibular angle to chin along inferior border of mandible; anterior line, anterior border of masseter; posterior line, posterior border of masseter. These four lines create a parallelogram. The boundaries of the safe zone within the parallelogram lie 1cm from each of the lines (area of darker blue shading). They therefore stay away from the facial artery and vein and parotid gland as well as the major branches of the facial nerve

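### For TAU participants still on medication at week 36, the Table 2 reaction window, the taper rule and the week 37 call do not fit together, and the protocol disagrees on who gets that call

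*Protocol*

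**What the plan says.** Section 9.2 makes a reporting period for serious adverse reactions (SARs) mandatory: "All SARs occurring from the 1st dose of IMP to the time periods specified in table 2 must be reported to NCTU". Table 2 gives that period as "Time period from last trial dose (including any tapering dose) for end of SAR monitoring/days", and the entry is 7 days for each of the four drugs. After it, reporting becomes passive: "Following this defined active monitoring period for SARs, investigators are still required to report any SARs or SUSARs they become aware of".

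Section 8.4 says that, outside an emergency, the quickest "allowed discontinuation would be spread over 4 weeks or slower for amitriptyline and gabapentin". It adds that tapers lasting months are permitted.

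Three places bear on the last safety contact:

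- Section 7.4.4: "The research team will contact the patient by telephone 7 days after the 36 week visit to identify any adverse events". No arm or treatment status is named.
- Schedule of Events (7.4.10): the call is in a week 37 (+3 days) column, and footnote g reads "Only required if participant still receiving TAU IMP at week 36 or stopped IMP after week 35".
- Trial Summary: "AE or SAE reporting from informed consent up to 36 weeks".

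Section 9.2 itself runs adverse event (AE) and SAE recording to the end of trial participation. Section 7.9 returns participants to routine care at week 36, leaves any continued TAU to the treating clinician, and makes no provision for further trial medication. Footnote e of the schedule puts the final pregnancy test 7 days after week 36 for participants still on TAU.

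**The concern.** There are two separate problems.

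The first concerns TAU participants still taking medication at week 36, a group that footnote g expects to exist. Table 2 counts tapering doses, and section 8.4 makes a taper last at least 4 weeks. A single call one week after week 36 would then come while the participant is still taking the drug, before the 7-day period has begun. Table 2 calls for active monitoring of SARs over a stretch in which the schedule plans no contact.

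The second concerns who is called. Sections 7.4.4 and 7.4.10 name different groups, and the Trial Summary implies that AE reporting has already ended. Under footnote g, whether a participant has an extra week of AE collection depends on arm and, within TAU, on treatment status after randomisation. That matters because comparing the adverse effect profiles of the interventions is a stated secondary objective. The trial is open label, so unequal questioning about events is best avoided where it can be avoided cheaply.

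**Working it through.** **Table 2's own figure.** The rule is 5 × half-life, rounded up to whole weeks.

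- Amitriptyline: 5 × 25 h = 125 h = 5.2 days, rounds up to 7 days. The table prints 155 h, a slip, but 155 h also rounds up to 7 days.
- Gabapentin: 5 × 7 h = 35 h = 1.5 days, rounds up to 7.
- Lidocaine: 5 × 1.68 h = 8.4 h = 0.35 days, rounds up to 7.
- Botox: 5 × 10 h = 50 h = 2.1 days, rounds up to 7.

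The 7-day entry therefore reproduces for all four drugs.

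**Window against last contact.** Inputs: week 36 = 36 × 7 = day 252; call at 252 + 7 = day 259, up to day 262 with the 3-day allowance; minimum taper 28 days (8.4); window end = last dose + 7 days (Table 2). Visit 5 is taken on its nominal day. Moving it within its ±7-day allowance moves the call by the same amount, so the gap for a taper starting at that visit is unchanged.

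| Case | Last dose (day) | Window ends | Against call at day 259–262 |
|---|---|---|---|
| TAU, 4-week taper starts at week 36 | 252 + 28 = 280 | 287 (week 41) | 287 − 262 = 25 to 287 − 259 = 28 days after the call |
| TAU, 12-week taper starts at week 36 (assumed length, for illustration) | 252 + 84 = 336 | 343 (week 49) | 81 to 84 days after the call |
| TAU, last dose at week 36 | 252 | 259 (week 37) | covered |
| TAU, last dose at week 35 | 245 | 252 (week 36) | covered |
| Injection arms, last cycle at week 24 or 25 | 168 or 175 | 175 or 182 | covered by the week 36 visit |

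In the first case the period from week 36 to the close of the window is 28 + 7 = 35 days, of which 25 to 28 have no planned contact. For a 4-week taper to be finished by week 36, it would have to start by day 252 − 28 = 224, that is week 32, before the primary assessment.

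**Who is followed, and for how long.** Setting the passages side by side:

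| Passage | TAU, still on drug at week 36 or stopped after week 35 | Other TAU | Injection arms |
|---|---|---|---|
| Trial Summary | week 36 | week 36 | week 36 |
| 7.4.4 | week 37 | week 37 | week 37 |
| 7.4.10, footnote g | week 37 | week 36 | week 36 |

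Under footnote g the difference is one week in 36 (1/36 = 2.8%) for the TAU participants called.

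**The case against.** The strongest reply is that Table 2 counts from the last trial dose, and trial dosing may end at week 36. Treatment duration is 36 weeks. Section 7.4.4 returns patients to their GP then, section 7.9 provides no further trial medication, and the schedule lists only a review of TAU medication at that visit. Footnote e uses the same week-36-plus-7-days logic. On this reading the window closes at week 37, when the call takes place, and the mention of tapering doses serves people who stop and taper during the 36 weeks. This is a coherent reading and may be the intended one. But the protocol never states it, and Table 2's wording makes no exception for a taper that runs past week 36.

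A reader might go further and infer three things that the documents do not support.

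- That the window is never reached. It is reached in both injection arms and for TAU participants whose last dose, taper included, falls by week 36.
- That sites cannot obey both Table 2 and the schedule. Table 2 sets a reporting period and prescribes no contact at its end. A site can make the call and still report a later SAR, and section 9.2 requires reporting of those it learns of even after the window.
- That most or all of the TAU arm is affected and TAU harms are understated. No document says how many will still be on TAU at week 36 or will start a taper then, and section 7.9 foresees some continuing. Table 2 governs SARs, not all AEs. The Liverpool profile is collected in every arm at weeks 12, 24 and 36 and is untouched.

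The contradiction over who is called stands on either reading. A common AE cut-off could be set in the statistical analysis plan, which is not at hand, but that would not settle what sites are told to collect.

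**Conclusion.** The point holds in two limited parts.

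First, for TAU participants still on medication at week 36, Table 2, section 8.4 and the week 37 call are inconsistent as written. If doses after week 36 are trial doses, the window closes at week 41 or later, at least 25 to 28 days after the last planned contact. This assumes a taper of the minimum length starting at the week 36 visit. If they are not trial doses, there is no monitoring gap and the fault is confined to Table 2's wording. The number of participants concerned cannot be derived from the protocol.

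Second, and independently, section 7.4.4, footnote g and the Trial Summary give different AE collection periods, and footnote g makes the period differ by arm. The numerical effect is small, one week in 36, and events up to week 36 are unaffected. It is still an avoidable ambiguity in a mandatory procedure and should be corrected.

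**What to change.** Reconcile the Trial Summary, 7.4.4, footnote g in 7.4.10, 7.9, 8.4 and Table 2 in 9.2:

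1. State whether doses taken after week 36 count as trial doses, and make the Table 2 window and the last safety contact agree with that statement.
2. Make 7.4.4 and footnote g name the same participants for the week 37 call, and bring the Trial Summary's AE period into line.
3. Compare AEs between arms up to a common week 36 cut-off, and list later events separately.

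The 155 h entry in Table 2 can be corrected to 125 h at the same time, with no consequence for the window.

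The cost is protocol wording and one line on the AE comparison. If the sponsor decides that doses after week 36 are trial doses, a later contact would be needed, and that is not clearly cheap: a taper run by the GP may last months and has no fixed end date. It is therefore not made a required part of the fix. Which reading is right is for the sponsor to decide, and no change to the taper or to any other clinical rule is proposed.
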